8.10 Plans for Interim Analysis

There are no formal interim analyses that are designed to potentially stop or change the study design. An interim summary analysis of the EMG data may take place when approximately 15 subjects in each treatment group have been treated for the purpose of a publication. Along with the BMG data, key demographic and operative endpoints will be

summarized. There is no intention to utilize this interim analysis as a means to justify stopping the study early.

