10.10 Interim Analysis

There are no planned interim analyses for the purpose of stopping the study early. However, some statistical analyses may be performed for conference presentations or abstracts prior to the primary endpoint being reached.

11 Data Management

Electronic Case Report Forms (eCRFs) entered into an electronic data capture (EDC) system will be used to collect all Subject data once a Subject is enrolled in the study. Study sites will be asked to enter Subject data into the eCRFs via the EDC web-based database portal promptly after each subject is enrolled.

For all Subjects, detailed information related to the primary diagnosis, anesthesia type and time, and surgical exposure (*e.g.,* anterior approach), and other surgical variables will be recorded on the Operative Details eCRF. Product code details for each implant and study article (KINCISE adapters as applicable) used during the procedure must be recorded on the Device Log eCRF.

Data collected during the study for each Subject will be maintained as accurately and completely as possible with entries into an EDC system provided by DePuy Synthes. The personal data recorded on all documents and within the EDC system will be regarded as confidential. The Investigator will be responsible for the timing, completeness and accuracy of the details entered within the EDC system. All data entered in the database must have source documents in the Subject's medical records.

The Investigator should retain copies of all documents pertaining to this study (including source documentation, the informed consent document and any other documents to identify the Subjects) for at least two years after this clinical investigation is completed. In addition, if the Investigator moves/retires, etc., she/he should provide DePuy Synthes with the name and address of the person who will be responsible for the Subjects' study related records.

12 Study Implants

The Pinnacle Hip Solutions[®] (Pinnacle cup) system was first launched in 2000. Multiple configurations are now available (see Table 12-1 below).

Cup Style	Image	Description
100		 POROCOAT[®], DUOFIX[®] or GRIPTION[®] coating Available in sizes 48-66 mm (44 & 46mm available in GRIPTION)
Sector		 Three screw holes for optional adjunct fixation - screw hole pattern allows screw access to the ilium and posterior column POROCOAT, DUOFIX or GRIPTION coating Available in sizes 48-66 mm

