Sticker sheets were created, one set for up to 30 sites, containing treatment assignments for 120 subjects using a fixed block size of 4 and a treatment allocation ratio of 1:1. On the face of each sticker is a character in the sequence A, B, C,, X, Y, Z, AA, AB, AC,AX, AY, AZ, BA, BB, BC, etc...., BX, BY, BZ, CA, etc...

The stickers should be removed sequentially to reveal the randomization code and treatment group ('Study (Kincise)' or 'Control (Mallet)') for each consecutive consented subject that meets eligibility criteria. Peeled sticker should be placed on the screening log to document that randomization was unbiased. The planned randomization group should then be documented in the applicable source document and on the Randomization eCRF (eCRF RDM) in the database.

The assigned treatment will remain secret to site personnel until subject is found to meet all eligibility criteria; No other blinding is implemented in this study.

4 Interval Windows

The study includes the following periods: Pre-op, Operative, Immediate post-op, 6 Week, 24 Week. Intervals related to each are shown in Table 3, below.

Visit	Minimum Day	Maximum Day	Midpoint Day
Pre-Op	-180	0	
Operative	0	0	0
Immediate post-op	0	Discharge	
6 week	14	60	37
24 week	61	200	130

 Table 3
 Interval Windows for Non-Radiographic Study Visits

Time point specific data collected to satisfy the primary and secondary efficacy-related objectives will be assessed for compliance with these intervals. Only data which can be attributed to the visit intervals in Table 3 will be used in the analysis of primary and secondary endpoints. This visit will be hereafter referred to as the Analysis Visit and the originally recorded visit as the Nominal Visit. If multiple measurements fall into the pre-operative window, or into the 'Immediate post-op' post-operative window, the result collected most proximate to surgery will be utilized. For the '6 week' and '24 week' visits, if multiple measurements fall into the window will be utilized for analysis.

5 Levels of Significance

The level of significance is 95%. Primary endpoint analyses, further described in section 8.7, and secondary endpoint analyses with hypotheses, further described in 8.8, will use 1-sided 95% confidence intervals and associated p-values. Data summaries of secondary endpoints without hypotheses and of exploratory endpoints will use 2-sided 95% confidence intervals and associated p-values.

6 Analysis Sets

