8.1 General Conventions

All statistical analyses will be performed using SAS® Version 9.4 or higher, unless otherwise noted. Standard descriptive summaries for continuous data include the number of subjects with non-missing observations (n), mean, standard deviation (SD), median, minimum, and maximum values. For categorical data, the count and percentage will be provided. Percentages will be based on the number of subjects without missing data. If exploratory tests of hypotheses are performed, t-tests will be performed for continuous variables, and Fishers' Exact Test will be performed for categorical variables. Baseline for the Forgotten Joint Score is 6 weeks. Baseline for all other endpoints is the pre-operative

measurements collected before surgery. Unless specifically stated otherwise, all endpoints will be analyzed first by treatment then combined.

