8.4 Operative details

Operative details will be summarized for the subjects in the Safety Analysis Population and for the subjects in the Per Protocol population (both in total and by treatment group):

- Primary diagnosis;
- Occurrence of Intraoperative complication(s) (Y/N);
- ASA Risk;
- Surgical time (Duration) (min);
- Anesthesia time (Duration) (min);

- Femoral broaching time (Duration) (min);
- Surgical approach;
- Use of Hana table
- Use of standard table if Hana table was not used
- Use of intraoperative fluoroscopy to position the cup
- Starting broach size;
- Ending broach size;
- Skipped any broach size (Y/N); If any broach sizes were skipped then provide a listing of which sizes were skipped;
- Use of KINCISE (Yes/No);
- Listing of steps taken when KINCISE was used;
- Use of a mallet;
- Listing of steps taken when mallet was used;
- Use of wires/cables (Y/N);
- Use of screws (Y/N);
- Listing of additional details when screws were used;
- Cup need to be repositioned after the initial impaction (Y/N);
- Use of KINCISE when cup was needed to be repositioned after the initial impaction (Y/N);
- Established preoperative target(s) for inclination during the surgery was changed (Y/N);
- New target in degrees if established preoperative target(s) for inclination during the surgery was changed;
- Established preoperative target(s) for version during the surgery was changed (Y/N);
- New target in degrees if established preoperative target(s) for version during the surgery was changed;
- Acetabular bone graft;
- Acetabular bone class;

- Acetabular osteophytes removed (Y/N);
- Femoral bone graft;
- Femoral bone class proximal;
- Femoral bone class distal;
- Femoral DORR class;
- Femoral stem component present (Y/N);
- Femoral head component present (Y/N);
- Acetabular shell (cup) component present (Y/N);
- Acebabular liner (insert) component present (Y/N);
- EMG data uploaded to Athos (Y/N).

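### Early publication or conference reports could disclose broaching and surgical times by arm to unblinded surgeons while enrolment continues, and no rule requires these times to be pooled or withheld

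*SAP*

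**What the plan says.** SAP 8.10 plans no formal interim analysis that could stop or redesign the study. It does allow one early summary, with publication as its stated purpose: "An interim summary analysis of the EMG data may take place when approximately 15 subjects in each treatment group have been treated". It adds: "Along with the BMG data, key demographic and operative endpoints will be" summarised (BMG looks like a slip for EMG). It does not list those operative endpoints, say whether they are shown by arm or pooled, or say when the paper may appear.

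Three other SAP sections bear on how the gap would be filled:

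- SAP 8.1 sets the general convention that, absent a specific exception, "all endpoints will be analyzed first by treatment then combined". SAP 8.10 states no exception.
- SAP 8.4 includes femoral broaching time and surgical time among the operative details, which are to be summarised in total and by treatment group.
- SAP 3 conceals the assignment until eligibility is confirmed, and then says: "No other blinding is implemented in this study".

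Protocol 10.10 adds a second route: "some statistical analyses may be performed for conference presentations or abstracts prior to the primary endpoint being reached". It names no endpoint and excludes none. Neither document contains an embargo or a pooled-only rule for such reports, and SAP 9 says there is no data monitoring committee.

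**The concern.** The primary endpoint is a duration that the operating surgeon controls. Protocol 4.1 runs the clock from the box osteotome entering the femoral canal to the seating of the final broach trial, and the surgeon knows which instrument is in use. A cross-site comparison of broaching time by arm, released while cases remain to be done, tells those surgeons how the trial is going on the quantity they produce. It could change the effort or pace they bring to one arm.

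Any such change would feed straight into the non-inferiority comparison. The plan has little that would reveal it: SAP 8.13 plans no sensitivity analyses and SAP 8.15 no formal assessment of site homogeneity.

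**Working it through.** **Inputs.** SD of broaching time 2.5 min, margin 1.25 min, one-sided alpha 0.05, 200 per arm (Protocol 10.8, SAP 7). SD of skin-to-skin OR time 7.5 min, margin 3.75 min (same sections). Early summary at about 15 per arm (SAP 8.10).

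**1. The plan's own figures.** With a true difference of zero, the noncentral t gives 95.1% power at 88 per arm (94.9% at 87), which matches the stated 88 for 95% power. At 200 per arm the power is 99.96%, which matches the stated figure of more than 99%. The inputs are therefore being read as the plan intends.

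**2. How early the summary falls.** 2 × 15 = 30 treated, and 30/400 = 7.5%. At most 400 − 30 = 370 subjects (92.5%) would remain.

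**3. How precise the comparison would be.**
- Broaching time: SE = 2.5 × √(2/15) = 0.913 min. The two-sided 95% half-width is t(28; 0.975) × 0.913 = 1.87 min, against a margin of 1.25 min.
- OR time: SE = 7.5 × √(2/15) = 2.74 min. The half-width is 5.61 min, against a margin of 3.75 min.
- With no true difference, the chance that the observed broaching difference exceeds 1.25 min in one direction or the other is 2 × [1 − Φ(1.25/0.913)] = 2 × 0.0855 ≈ 17%.

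A by-arm result at this stage could suggest a margin-sized difference by chance alone.

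**4. How sensitive the final analysis is to a later shift.** The documents give no figure for a change in behaviour, so the shift b is an assumption, shown as a range. Suppose every one of the remaining 185 subjects per arm is affected, so that the later arm difference moves by b minutes in favour of KINCISE. The overall mean difference then moves by b × 185/200. The final SE is 2.5 × √(2/200) = 0.25 min. When the true difference equals the margin, the probability of wrongly concluding non-inferiority is Φ(b × 0.925/0.25 − 1.645):

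| Assumed b (min) | Shift in overall difference (min) | One-sided error at the margin |
|---|---|---|
| 0 | 0 | 5% |
| 0.1 | 0.0925 | about 10% |
| 0.25 | 0.231 | about 24% |
| 0.5 | 0.4625 | about 58% |

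A shift against KINCISE would instead make non-inferiority harder to show. The table shows sensitivity; it does not predict what would happen.

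**5. Whether by-arm broaching time falls within the early summary.** SAP 8.10 says operative endpoints accompany the EMG data, SAP 8.4 places broaching and surgical time under operative details, and SAP 8.1 makes by-treatment reporting the default. Together these permit by-arm disclosure and point towards it. They do not state it, because SAP 8.10 neither itemises its endpoints nor refers to SAP 8.4.

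**The case against.** The case on the other side has real force, and much of it stands.

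- **Both analyses are optional, and neither names broaching time.** This stands. For the EMG paper, by-arm broaching time is an inference from SAP 8.1 and 8.4. For conference reports the inference is weaker: SAP 8.1 governs the format of whatever is analysed, not its content, and Protocol 10.10 could be met by demographic summaries. A reader might infer that early conference material will show broaching time by arm. The text shows only that nothing prevents it.
- **Release during enrolment is not certain.** This stands. SAP 8.10 sets when the analysis may be done, with no publication date, and enrolment may take up to 12 months (Protocol synopsis). SAP 8.4 records whether EMG data were uploaded, so the 15 per group may count only subjects with EMG data and be reached after the 30th subject. Protocol 17 requires sponsor approval of manuscripts, so release is not automatic, although approval is not an embargo. The figure of 370 is therefore an upper bound.
- **Type I error.** A reader might infer that an early look inflates it through repeated testing. It does not. No interim test or stopping decision is planned, and a descriptive summary spends no alpha.
- **Patient selection.** A reader might infer that published times would distort which patients enter each arm. SAP 3 keeps the assignment concealed until eligibility is confirmed. While that holds, any change in case selection affects both arms alike.
- **Surgeons already know their own times with both instruments.** True, so some pace effect can exist without any publication, and the added effect of a noisy summary cannot be quantified from the documents. But a sponsor-approved comparison across sites is different information from a surgeon's own cases, and it can be withheld at almost no cost.

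**Conclusion.** The concern holds as a gap in protection. As written, the plan could disclose the primary endpoint and surgical time by arm to unblinded surgeons during enrolment, and neither document requires these times to be pooled or held back. Such a release can bias later broaching times; the documents do not show that it will.

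The size of any bias is unknown. What can be said is that the early comparison would have a 95% half-width of about 1.87 min against a 1.25 min margin, and that no more than 370 of 400 subjects could still be untreated. The final comparison, with an SE of 0.25 min, would be sensitive to a sustained shift of even a fraction of a minute. These figures rest on the planned SD of 2.5 min, on 15 per group meaning the first 30 treated subjects, and, for sensitivity, on an assumed shift in all later cases.

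This is a low-cost safeguard for the primary comparison. It is not a fault in the test or its error rate.

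**What to change.** In SAP 8.10 and Protocol 10.10, state that until the last index surgery is complete, femoral broaching time and skin-to-skin OR time will not be summarised or released by arm, and that any earlier EMG or conference report gives these times pooled over arms only. The surgical time listed in SAP 8.4 should be covered by the same sentence. Because SAP 8.1 yields to specific statements, a sentence in SAP 8.10 is enough to override the by-treatment default.

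The restriction need not run to database lock or extend to cup angles. Broaching and OR times are complete once the last index surgery is done, and cup angles are not the times that the surgeon's pace determines.

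The cost is a sentence in each document, with the protocol change submitted to the IRBs under Protocol 15.6. The one real loss is that an early EMG paper would carry no comparative operative times.

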8.11 Handling of Missing Data

Only subject data which is collected in the study will be utilized in analyses; there will be no imputation of missing data.

8.12 Adjustment for Multiplicity

A gatekeeping strategy will be utilized to ensure the family-wise type I error rate does not exceed 5% for all pre-specified hypotheses: the test of non-inferiority of the primary endpoint will be performed at the 95% confidence level and all subsequent hypotheses in the order specified in sections 8.7 and 8.8 will be tested only if the prior null hypothesis was rejected. P-values and confidence intervals for analyses which were not tested will not be adjusted for multiplicity and may only be provided to facilitate clinical judgement.

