The following analysis sets are defined:

- Enrolled The Enrolled population set will consist of all subjects who sign the informed consent document.
- Safety The Safety population set will consist of all subjects in the Enrolled population set for whom treatment was attempted, according to the actual treatment received.
- Per Protocol The Per Protocol population set will consist of all subjects in the Enrolled population set who successfully received the planned treatment, who met all inclusion/exclusion criteria, who were seen at least once at a post-operative visit, and who did not have any protocol deviations which were prospectively determined to potentially have influence on the scientific validity of the data (such as inclusion/exclusion criteria).

7 Sample Size Justification

Primary endpoint Non-Inferiority (NI) analysis: Based upon input from key opinion leaders (KOLs) and data from other studies, typical femoral broaching time with manual instruments is anticipated to have a range of 5 to 15 minutes, which implies a standard deviation of approximately 2.5 minutes (1/4 of the range). Moreover, KOLs suggest that a difference of 10 minutes in femoral broaching time (increase for a single patient) is clinically meaningful. The non-inferiority margin of 1.25 minutes was established because it Page 8 of 29

is ½ of the anticipated standard deviation and is much less than a clinically meaningful difference. Under a 1-sided test with 5% alpha, a sample size of N=88 per group would be sufficient to demonstrate non-inferiority with 95% power. A sample of size N=200 per group (N=400 total) was chosen as feasible by the sponsor and desirable for providing further data for both KINCISE and Anterior Advantage; this sample size would provide more than 99% power to demonstrate non-inferiority for the primary endpoint analysis.

Primary endpoint supplemental superiority analysis: It is not known if there will be a true difference in means between groups. However, if there is a true difference of 1 minute between group means (lower time favoring KINCISE), and assuming an SD as stated above (2.5 minutes), then a sample of N=200 per group (N=400 total) would provide approximately 99% power to demonstrate superiority.

Secondary endpoint analyses:

• Non-inferiority of skin-to-skin OR time

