8.7 Primary Endpoint and Associated Hypotheses

The primary endpoint analysis is to demonstrate that femoral broaching time (in minutes)

with KINCISE is non-inferior to femoral broaching time with manual instruments (not using KINCISE) under a non-inferiority margin of 1.25 minutes.

Hypotheses for this non-inferiority analysis are as follows:

- Null Hypothesis: $H_0: \mu_I \ge \mu_C + 1.25$
- Alternative Hypothesis: H_A : $\mu_I < \mu_C + 1.25$

where μ_I and μ_C are mean femoral broaching times with and without KINCISE, respectively, and 1.25 is the NI margin. The null hypothesis will be rejected and non-inferiority will be concluded if the 1-sided upper 95% confidence limit for the $\mu_I - \mu_C$ difference (based upon a 2-sample t-test) is less than 1.25. The study will be deemed to be successful if this analysis demonstrates non-inferiority of femoral broaching time.

If non-inferiority is successfully demonstrated, then a test for superiority will be conducted to assess if femoral broaching time with KINCISE is less than femoral broaching time without KINCISE with statistical significance (1-tailed t-test with 5% alpha).

The primary endpoint analysis and all associated hypotheses will be conducted on the Per Protocol Analysis Set.

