8.8 Secondary Endpoints and Associated Hypotheses

All secondary endpoint analyses and associated hypotheses will be conducted on the Per Protocol Analysis Set.

If the primary endpoint analysis successfully demonstrates non-inferiority of femoral broaching time, regardless of whether the above test of superiority was successful or not, then the following three secondary endpoint analyses will be conducted under a gatekeeping strategy, in this specified order, where testing is performed in sequence and continues until a null hypothesis is not rejected or all hypotheses have been tested, each with a 1-sided alpha of 0.05:

- 8.8.1 Skin-to-skin OR time
 - Skin-to-skin OR time in minutes will be summarized as a continuous variable for both treatments and combined
 - A non-inferiority test of skin-to-skin OR time will be conducted with a noninferiority margin of 3.75 minutes, using a 2-sample t-test:
 - Null Hypothesis: $H_0: \mu_I \ge \mu_C + 3.75$
 - Alternative Hypothesis: H_A : $\mu_I < \mu_C + 3.75$
 - where μ_I and μ_c are mean skin-to-skin OR times with and without KINCISE, respectively. The null hypothesis will be rejected and non-inferiority will be concluded if the 1-sided upper 95% confidence limit for the μ_I μ_c difference (based upon a 2-sample t-test) is less than 3.75
 - The 1-sided upper 95% confidence limit for the difference and the pvalue will be presented.
- 8.8.2 The percent of subjets with acetabular cup abduction angle within +/- 10 degrees of plan
 - The proportion of subjets with acetabular cup abduction angle within +/- 10 degrees of plan will be summarized for both treatments and combined
 - A non-inferiority test of the percent of subjects with acetabular cup abduction angle within +/- 10 degrees of plan under a NI margin of 10% will be conducted:
 - Null Hypothesis: $H_0: P_I \le P_C 10\%$
 - Alternative Hypothesis: $H_A: P_I > P_C 10\%$
 - where P_I and P_c are the percentages of subjects with acetabular cup abduction angle within 10% of plan with and without KINCISE, respectively. The null hypothesis will be rejected and non-inferiority will be concluded if the 1-sided lower 95% confidence limit for the P_I –

 P_{C} difference (based upon a normal approximation method) is greater than -10%

- The 1-sided lower 95% confidence limit for the difference and the pvalue will be presented.
- 8.8.3 The percent of subjects with acetabular cup version angle within +/- 10 degrees of plan

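### SAP 8.12 promises family-wise error of at most 5%, but the order in 8.8 allows up to about 9.75%, and the order in 8.12 itself would break the 88% success figure

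*SAP*

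**What the plan says.** SAP 8.12 makes the claim about error control: "A gatekeeping strategy will be utilized to ensure the family-wise type I error rate does not exceed 5% for all pre-specified hypotheses". It then gives the order of testing: "all subsequent hypotheses in the order specified in sections 8.7 and 8.8 will be tested only if the prior null hypothesis was rejected".

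SAP 8.7 contains two tests of broaching time: non-inferiority at a 1.25-minute margin and, if that succeeds, superiority "with statistical significance (1-tailed t-test with 5% alpha").

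SAP 8.8 opens the secondary sequence (skin-to-skin time, cup abduction, cup version) once primary non-inferiority is shown, "regardless of whether the above test of superiority was successful or not", with the tests run "each with a 1-sided alpha of 0.05". Protocol 10.5.2 has the same rule.

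SAP section 7 multiplies four non-inferiority powers, (99%)(99%)(95%)(95%), to give an overall likelihood of at least about 88%. Superiority is not one of the factors. The table of changes in SAP section 10 corrects one word of the gatekeeping rule (alternative becomes null) and leaves the order as it was.

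**The concern.** Two sequences are each sound alone. Non-inferiority followed by superiority on the same parameter costs no extra alpha, and neither does a fixed sequence of secondary tests after primary non-inferiority. Under SAP 8.8, however, both run behind the same first test, each at the full one-sided 5%, and neither depends on the other. This is not a single fixed sequence, and no alpha is divided or passed between the branches. If superiority and a secondary null are both true, there are two separate chances of a false claim.

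SAP 8.12 describes something else. Superiority is the last test in 8.7, so requiring each prior null to be rejected means that a failed superiority test ends testing before the secondary endpoints. In that situation 8.8 requires the secondary tests and 8.12 forbids them. Under the first rule the 5% statement is untrue; under the second the 88% statement is untrue. With both rules on file, the choice could be made after the superiority result is known.

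**Working it through.** **Inputs (SAP section 7 unless noted).** Broaching time: "The non-inferiority margin of 1.25 minutes was established", and the range "implies a standard deviation of approximately 2.5 minutes (1/4 of the range"). OR time: margin 3.75 min, SD 7.5 min. Cup endpoints: margin 10 percentage points, anticipated success 90–95% (abduction) and 91–92% (version). 200 per group; all tests one-sided 5%, critical value 1.645.

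**1. Reproducing the plan's figures.**
- The plan says that "a sample size of N=88 per group would be sufficient to demonstrate non-inferiority with 95% power". With a true difference of 0, n = 2 × (1.645 + 1.645)² × 2.5² / 1.25² = 86.6, so 87; a t-based calculation gives 95.1% power at 88. The stated size therefore rests on a true difference of zero.
- At 200 per group the standard error for broaching time is 2.5 × √(2/200) = 0.25 min. Primary non-inferiority power is Φ(1.25/0.25 − 1.645) = 99.96%. OR time has the same ratio of margin to SD, so also 99.96%.
- Superiority power at 1 min is Φ(1/0.25 − 1.645) = 99.1%.
- Cup power (unpooled normal approximation) is 95.4% for abduction at 90% and 96.8% for version at 91%.
- 0.99 × 0.99 × 0.95 × 0.95 = 88.45%. The plan's figure reproduces.

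**2. Family-wise error under SAP 8.8.** Let G be the probability of passing primary non-inferiority and S that of rejecting in the superiority test. With one secondary null true at its margin and independent statistics, error = S + (G − S) × 0.05.
- True broaching difference 0, OR-time difference 3.75 min: 0.05 + (0.9996 − 0.05) × 0.05 = 9.75%, the same as 1 − 0.95².
- Broaching time is part of OR time, so positive correlation is likely. Neither document gives a value. Assumed correlations of 0.3, 0.5 and 0.6 give 9.3%, 8.8% and 8.4%.
- With OR time truly non-inferior and a cup endpoint at its margin (independence assumed), simulation of 400,000 trials gives 10.0% for abduction and 9.9% for version. These slightly exceed 9.75% because the normal approximation for proportions is a little liberal.
- If KINCISE is truly 0.1 min slower, S = Φ(−1.645 − 0.4) = 2.04% and G = 99.84%, so error is 0.0204 + 0.9780 × 0.05 = 6.9%. At 0.25 min slower, S = 0.41% and G = 99.07%, giving 5.3%. If KINCISE is truly faster, the superiority null is false and 5% holds.

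**3. Overall success under SAP 8.12.** Family-wise error is 5% (simulated 5.0%), but superiority becomes a further condition. Multiplying the plan's 88.45% by superiority power:

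| True advantage | Superiority power | Overall success |
|---|---|---|
| 0 min | 5.0% | 4.4% |
| 0.5 min | 63.9% | 56.5% |
| 1 min | 99.1% | 87.6% |

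Using the recomputed powers instead of the plan's rounded ones, simulation gives 4.5%, 59% and 91%, against 91.9% under 8.8 with no true difference.

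**The case against.** The best defence is that 8.12 defers to 8.8. It cites the order in 8.7 and 8.8, and 8.8 expressly detaches the secondary tests from superiority. Protocol 10.5.2 says the same, Protocol 4.2 and the synopsis open the secondary sequence on primary non-inferiority alone, the sample-size section calls superiority supplemental, and the 88% product omits it. On that reading the 88% stands. This is the more likely intention, and the two consequences are alternatives that cannot both occur. But this reading leaves the 5% statement false, because superiority is pre-specified and 8.12 covers every pre-specified hypothesis.

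Second, 9.75% is a worst case. It needs a true broaching difference of zero and a secondary endpoint exactly at its margin, and the excess nearly vanishes once KINCISE is 0.25 min slower. That is correct and should be said when the figure is quoted. It does not rescue the claim: a guarantee that error does not exceed 5% is judged at its worst case, and zero difference is the plan's own sizing assumption.

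Third, study success depends only on primary non-inferiority, which is tested first and keeps its 5% error rate under either rule. That stands. The defect is confined to the superiority and secondary claims, and the family-wise statement appears only in the SAP.

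**Conclusion.** The concern holds. Under SAP 8.8 and Protocol 10.5.2 family-wise error can reach about 9.75%, against a stated maximum of 5%. This assumes no true broaching difference, one secondary endpoint at its margin and independent statistics; for OR time with an assumed correlation of 0.3 to 0.6 it is 9.3% to 8.4%. Under the literal order in SAP 8.12 the error rate is 5%, but the 88% becomes about 4% with no true broaching difference and about 56.5% at 0.5 min. It survives only near the 1-minute benefit, and the plan says it does not know whether a difference exists. No single reading makes both statements true. This should be settled before analysis because the two rules diverge exactly when superiority fails.

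**What to change.** State one testing order, identically, in SAP 8.7, 8.8 and 8.12, and align Protocol 4.1, 10.5.1, 10.5.2, 10.9.3 and the synopsis, or record the departure in SAP section 10.

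- **Preferred: one fixed sequence with superiority last.** Primary non-inferiority, skin-to-skin time, abduction, version, then superiority, each at one-sided 5%. Family-wise error is at most 5% and the 88% is unchanged. Cost: superiority can be claimed only after the cup endpoints pass, so its power at a 1-minute benefit falls from 99% to 0.8845 × 0.991 = 87.6% on the plan's rounded powers (about 91% on recomputed ones).
- **Alternative: split alpha after primary non-inferiority**, 2.5% to superiority and 2.5% to the secondary sequence. Nominal error is at most 5% (1 − 0.975² = 4.94% if independent; simulated 5.2% with abduction at its margin, again from the normal approximation). Powers are 97.9% for superiority at 1 min, 99.9% for OR time, 91.5% for abduction at 90% and 93.8% for version at 91%. The full secondary sequence has about 86%, so the 88% figure would need restating.
- **Minimum: narrow the claim.** Keep the 8.8 order, limit the 5% statement to primary non-inferiority and the three secondary tests, and label superiority as outside the controlled family. This costs no power, but a superiority result would lack family-wise protection.

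Each option changes wording only, with no change to sample size or data collection.
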